5 INTRODUCTION

5.1 Background and study rationale

Lumentin® 44 is being developed as a novel oral contrast medium to be used in diagnostic examinations of the abdomen. Initial clinical development has focused computerized tomography (CT) (Leander et al., 2022; Leander et al., 2022) while the present trial aims to explore if the signal characteristics of Lumentin® 44 is favourable in Magnetic resonance enterography (MRE), a specialized type of magnetic resonance imaging (MRI) performed with a contrast material to produce detailed images of the small intestine.

Oral contrast agents are used prior to abdominal CT (abd-CT) and CT of the small bowel (CT-enterography, CTE) to demarcate bowel loops from its surroundings and to create a difference in density between the bowel and other structures in the abdomen. Till now, the only contrast agents available and used for diagnosis in abd-CT are positive, with Hounsfield Units (HU) around +80, or neutral, i.e., with HU around and above zero. Both agent types provide CT-images with unsatisfactorily low contrast between the wall and lumen of the small intestine. Hence, there is a considerable need for a bowel filling contrast agent with true negative HU that would offer notably larger lumen-to-wall contrast, a prerequisite for improved mucosal lesion detectability.

A phase II study have been performed using Lumentin® 44 as a contrast agent for CT with encouraging results (Leander et al., 2022). If the same product can also be used in MRE assessment it would be an advantage for a radiological department to only handle a single oral small bowel filling contrast medium for both modalities CT and MRI. In addition, Lumentin® 44 has shown to have a favourable safety profile and may be a more tolerable alternative to the oral media used today in both CT and MRI. This proof-of-concept (PoC) trial is performed in healthy volunteers (HVs) with the aim to show that Lumentin® 44 can be used as an oral, small bowel filling contrast agent for MRE.

5.2 Lumentin® 44

Lumentin® 44 is a novel, HU-negative contrast agent which is formulated as a powder for oral foam. The powder product contains egg white protein (EWP) as foaming agent, xanthan gum as stabiliser, phosphate salts as buffering agents, and flavouring.

Prior to use, the powder is mixed with water and whipped to a stable foam, containing 44% v/v air and less than 4 % w/w dry matter, which is orally administered. The whipped, ready to use Lumentin® 44 foam is stable with suitable characteristics (air content, volume, bubble size, homogeneity, consistency, stability and palatability) for at least 2 hours.

The air trapped in the foam is the radiological key component that causes improved bowel lumen-to-wall contrast, with the interface at the surface of the mucosal lining of the bowel wall. The external demarcation of the small bowel from surrounding organs is on par with standard filling agents used in abd-CT examinations of today, but mesenteric vessels bordering the bowel wall are radiologically better visualized when loops are filled with Lumentin® 44. The reason for this is fewer image artefacts compared to diluted Omnipaque® (Omnipaque) in the gastrointestinal tract (GI) tract.

5.3 Clinical development to date

A previous formulation of the agent, Lumentin® 60 (60% v/v air), has been tested in a pilot Investigator initiated trial, approved by the local ethics committee and local institute of radiation protection (ref 1). The results were validated by 4 external reviewers and showed that Lumentin® 60 in its bowel filling capacity was on par with contemporarily used bowel filling agents (Omnipaque and Movprep®, Movprep). Furthermore, it was superior in contrast between bowel lumen and wall and revealed a favourable profile of side effects with no or only mild symptoms such as burping and fullness with preserved bowel consistency. The promising results obtained with Lumentin® 60 encouraged improved formulation, leading to Lumentin® 44, and continued clinical development to further explore the clinical importance of the improved contrast between bowel lumen and bowel wall with Lumentin® 44. A second goal for the new formulation was to guarantee high patient acceptance.

Lumentin® 44 has been investigated in two phase II trials:

In the completed and reported LUM-001 trial (Leander et al., 2022), the relative mean difference in contrast density shown on abdominal CT-images when using the contrast agent Lumentin® 44, was compared with abdominal CT-images using diluted Omnipaque and with abdominal CT-images using Movprep in subjects referred to computerized tomographic X-ray examination of the abdomen or thoraco-abdominal CT-examination.

Evaluation of clinical safety data confirm the favourable safety profile shown with Lumentin® 44. The difference in contrast density between bowel lumen and bowel wall was significantly larger after intake of Lumentin® 44 as compared with the comparator contrast agents Movprep and Omnipaque. There was no statistical difference in bowel filling properties. Neither was there any difference in diagnostic ability between Lumentin® 44 and Movprep or Omnipaque in this patient population (which had neither bowel disease nor bowel symptoms). The subjects' assessments of taste, smell, consistency, ability to swallow, and fullness placed Lumentin® 44 between Omnipaque and Movprep.

In trial LUM-002, the Radiological Crohn's disease Activity Score (RCDAS) of a CTE performed with Lumentin® 44 as a bowel filling contrast agent was compared with the RCDAS of a routinely performed MRE in patients with small bowel Crohn's disease. Evaluation of clinical safety data confirms the favourable safety profile shown in trial LUM-001. This trial has been completed but efficacy evaluation is ongoing.

Further details are available in the Lumentin® 44 Investigator Brochure (IB).

5.4 Risk-Benefit Assessment

EWP is widely used as a food ingredient. All excipients in Lumentin® 44, are of pharmacopoeia quality (buffer and stabiliser). The flavour complies with regulations concerning flavouring in food and food additives.

The side effects reported by subjects drinking up to 1.2 L of the Lumentin® 44 formulation in previously conducted trials indicate that Lumentin® 44 was well tolerated with only mild to moderate AEs reported.

Allergic reactions towards egg protein cannot be excluded and patients with a known sensitivity towards egg should not be exposed to Lumentin® 44.

Ingestion of a large volume of foam in a short time may have an impact on the resorption pattern of concomitant medications. Intake of other medications, which are absorbed in the small bowel, and having a narrow therapeutic window, should be avoided within a period of 4 hours before and until 1 hour after administration of Lumentin® 44.

Potential side effects associated with intravenous (IV) catheterization include insertion site pain, phlebitis, hematoma formation and infusate extravasation. Mechanical issues such catheter obstruction/occlusion and dislodgement may occur. The hospital sites staff is very familiar and alert to signs and symptoms of such complications, and preventive measures are in place, as well as intervention procedures for if/ when complications do occur. The IV catheter will remain in place for the duration of the visit 2 (day of MRE procedure), until collection of 8h blood sample.

The proposed Phase II study will enrol only HVs and as such no direct benefit is expected for the trial subjects.

Risks associated with Covid-19

Considering that the subjects in the trial will be HVs, the risk of contracting COVID-19, as part of the trial procedures is considered low.

All subject visits to the hospital will occur in facilities which are not used for patients with COVID-19. Procedures to prevent COVID-19 infection, as recommended by the Swedish "folkhälsomyndigheten", will be followed.

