7.3.2 Justification for Route and Dosage

A total of 73 subjects in previous clinical trials (LUM-001 and LUM-002) were asked to drink between 0.75 -1.5 L foam and the average amount drunk was 1026 mL of Lumentin® 44 foam. The amount of contrast agent that a subject can drink varies between subjects depending on e.g., age, weight, gender and medical condition. It is therefore necessary to define the recommended dose within a range.

This trial will recruit predominantly young HVs, and electrolyte levels will be investigated. The range is therefore narrower and the lower limit in the range is also higher than in previous trials. The lower limit in the dose range is set to 1.1 L. The recommended dose will be 1.2 L with the allowed upper range set to 1.5 L.

Sponsor: Lument AB

Clinical Trial Protocol

Protocol: LUMRIS-001, version 2.0 Final

CONFIDENTIAL

The route of administration is according to standard practice for an oral contrast agent.

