9 INVESTIGATIONAL PRODUCT AND PROCEDURES

9.1 Investigational product

Lumentin® 44 Powder for oral foam (Table 1) will be manufactured by Apotek Production & Laboratories AB, [name], Sweden and provided in labelled white sachets containing 17.4 g powder. Potable water (commercially available still water 0.5 L per bottle) for the preparation of the foam will be used.

Table 1: Lumentin® 44 Powder for oral foam

Ingredients	Concentration (g/sachet)
Egg White Powder	10.0
Sodium dihydrogen phosphate dihydrate (NaH ₂ PO ₄ • 2H ₂ O) ¹	1.0
Dipotassium phosphate (K ₂ HPO ₄) ¹	3.4
Xanthan gum ¹	2.5
Flavour ²	0.5

1) Ph. Eur.: European Pharmacopeia

2) The flavour complies with the regulations (EC) 1334/2008 and (EC) 178/2002 concerning flavouring in food and food additives.

Lumentin® 44 powder for oral foam will be delivered from APL to the clinical site, by order via the hospital pharmacy and stored temporarily at the site. The investigational product (Lumentin® 44 foam) is then prepared in-situ by adding 0.5 L potable water to Lumentin® 44 powder contained in one sachet, and the blend is then mixed to a stable foam in a dedicated preparation unit. The freshly prepared foam will be administered to the patient within 5 to 10 minutes as directed in the clinical trial protocol. The in-situ preparation will follow a procedure attached to the clinical trial protocol. The staff responsible for the in-situ preparation will be trained using the procedure and their training documented in the Trial Master File (TMF). Two sachets (0.9 L foam per sachet) will be required per subject.

For a detailed description of the preparation of Lumentin® 44 Foam (see Appendix 1 Lumentin® 44 : Lumentin 44 reconstitution protocol summary).

Lumentin® 44 Foam contains the same ingredients as Lumentin® 44 Powder for oral foam, see [Fel! Hittar inte referenskälla.](#), except for water added during the preparation.

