9.2 Dosage and Administration

The Investigational products will be taken orally by the subject during a period of 30 minutes - 1 hour.

A volume of 1.1 L to 1.5 L shall be consumed. A steady intake rate of the contrast agent is recommended to guarantee fullness of the gastrointestinal tract from stomach to terminal ileum of the small bowel.

The intake of the contrast agent will be stopped in case of an AE occurs or if the subject is unable to consume more than 1.1 L within 1 and ½ hour. The subject will be withdrawn in case the intake of the contrast agent has to be stopped.

The subject will be withdrawn from the trial if the maximum volume of the Investigational product taken by the subject is less than 1.1 L.

There is no risk of overdose.

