10.4 Precautions/overdose

Risks associated with intake of oral contrast agents include dysphagia with aspiration and secondary pneumonia. Although this trial intends to enrol only healthy volunteers and subjects with acute problems are excluded, a pre-emergency small bowel status might be aggravated to an established ileus by ingesting a large volume. Oral contrast agents should not be given to unconscious subjects, to those with swallowing disorders, or an acute abdomen problem.

Known sensitivity or allergy to contrast agent ingredients are exclusion criteria in clinical studies. However, unknown sensitivities or allergies might cause reactions that may need to be medically treated.

Intravenously administered Gd may cause allergic reaction of various severity from a mild rash to intensive care unit treatment. This is especially true for those with allergic reactions to a contrast agent earlier in life. Allergic reaction may be triggered in those with asthmatic bronchitis and treated with beta-blockers. Routines for handling these cases are well known to the staff which is regularly trained in dealing with emergency cases. Equipment for emergency care treatment is available at the clinic and the clinic is located in close proximity to the hospital emergency care department. Neither Buscopan nor Gd should be administered to patients with severe kidney failure.

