33. Make sure the water bottle is tightened enough to the connector and the bottle is placed at the lower position, so the water stays in the bottle.
34. Press the start button.
35. Flip the bottle to the top position.
36. Wait until L44 foam reconstitution is finished, which is indicated by the complete lightened LED lights on the HMI.
37. Flip down the water bottle.
38. Open the mixing chamber door.

39. Take out the mixing tool with a piece of kitchen paper towel underneath to contain the excess foam from the blade; wash the mixing tool quickly with tap water and dry it with kitchen paper towel. Install back the mixing tool to the CMPDU.
40. Take out the jar from the mixing chamber and close the door of the mixing chamber.
41. Fill in the AFTER FOAM PREPARATION section on the Whipping report_LUMRIS-001_V3.0.
42. GENTLY pour out L44 foam to the 1.5-L PET jar.
43. Take the 1.5-L PET jar with L44 foam and walk towards where the trial subject is sitting.
44. Give the trial subject the L44 foam in the 1.5-L PET jar and a small drinking cup.
45. Go back to the CMPDU.
46. Disconnect the empty water bottle if this is the last foam to prepare of the day; otherwise, leave the bottle connected before making a new foam with a new bottle of water.
47. Recycle the water tubing set back to Lument AB after the last foam of the day.
48. After the last foam of the day, hand wash the mixing tool with food-grade detergent and dry with kitchen tissue towel or wash the mixing tool in the dishwasher (foodstuff compatible is sufficient).
49. Wipe the mixing chamber if any visible L44 has dropped.
50. Power off the CMPDU at the end of the day (button on the back side of the CMPDU).
51. If there is any foam dropped onto the jar holder, press the cleaning mode button to let loose the jar holder.
52. Hand wash or wash in the dishwasher the jar holder.
53. Fix the jar holder back into the mixing chamber once it's cleaned.

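### The protocol caps the foam provided at 1.5 L, but its preparation steps hand each subject a nominal 1.8 L and nothing holds back the excess

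*Combined protocol and SAP*

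**What the plan says.** **Volume limits.** The synopsis (trial design) and section 7.1 say that up to 1.5 L (1,500 mL) is provided and that at least 1.1 L must be drunk. Section 9.2 gives the intake range as 1.1 to 1.5 L. Section 7.3.2 states: "The recommended dose will be 1.2 L with the allowed upper range set to 1.5 L".

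**Preparation and handover.** Section 9.1 states: "Two sachets (0.9 L foam per sachet) will be required per subject". Appendix 1 empties a whole sachet into the mixer, pours the foam into a jar and takes it to the subject (steps 20 to 22), then repeats this with the second sachet (steps 42 to 44). Each cycle ends: "Give the trial subject the L44 foam in the 1.5-L PET jar and a small drinking cup". Section 9.5 has the volume determined and the foam weighed before dispensing, with leftovers weighed afterwards. The only volume it names is the 1.1 L minimum.

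**Overdose.** Section 9.2 says: "There is no risk of overdose". Section 10.4, whose heading includes the word overdose, warns that "a pre-emergency small bowel status might be aggravated to an established ileus by ingesting a large volume". Section 12.6 repeats the warning in almost the same words.

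**Earlier experience.** Section 5.4 describes tolerability from "The side effects reported by subjects drinking up to 1.2 L of the Lumentin® 44 formulation in previously conducted trials". Section 7.3.2 says that the 73 subjects of LUM-001 and LUM-002 "were asked to drink between 0.75 -1.5 L foam and the average amount drunk was 1026 mL of Lumentin® 44 foam".

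**The concern.** The protocol's maximum and its dispensing steps do not agree. Staff who follow Appendix 1 exactly will give a subject more foam than the synopsis and section 7.1 say is provided, and neither the appendix nor section 9.5 tells them to stop or withhold at 1.5 L.

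This bears on the data as well as on conduct. Table 1 shows that the powder contains sodium and potassium phosphates, so the ingested load of the electrolytes measured as a secondary outcome rises in proportion to the volume drunk. The protocol says what follows if a subject drinks too little (withdrawal and replacement, section 8.3.2) but not what follows if one drinks more than 1.5 L. Section 13.3 does not address it either, so such a case would be left to the clean file meeting in section 13.5. With 10 subjects, one such case is a tenth of the data.

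The other two points concern the safety rationale for healthy volunteers, who expect no direct benefit (section 5.4). The overdose sentence and the large-volume warning have not been brought into line with each other. The tolerability statement also stops at a lower volume than this trial permits.

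**Working it through.** **1. Is 0.9 L per sachet a sound figure?** Inputs: 0.5 L water per sachet (section 9.1) and 44% air by volume (section 5.2).

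- Foam volume = liquid volume / (1 − air fraction) = 0.5 / (1 − 0.44) = 0.893 L.
- Assuming that the 17.4 g of powder adds 0.011 to 0.0174 L of liquid volume: 0.511 / 0.56 = 0.912 L, and 0.5174 / 0.56 = 0.924 L.

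All three values lie within 3% of the stated 0.9 L, so the protocol's figure is reproduced.

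**2. Volume handed over.**

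- Nominal: 2 × 0.9 = 1.8 L. The protocol does not print this total; it follows from section 9.1.
- Range from step 1: 2 × 0.893 = 1.79 L to 2 × 0.924 = 1.85 L.
- Excess over 1.5 L: 1.8 − 1.5 = 0.3 L, and 0.3 / 1.5 = 20%. Over the range it is 19% (1.786 / 1.5 = 1.19) to 23% (1.848 / 1.5 = 1.23).

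Some foam stays on the mixing tool. To bring the total down to 1.5 L, losses would have to reach 0.3 / 1.8 = 17% of what is made. The documents give no figure for this loss.

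**3. Are two sachets needed?** One sachet gives 0.9 L, below the 1.1 L minimum, so a second is required. Preparing 1.8 L is therefore not the error.

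**4. Does anything in the dispensing path set a ceiling?**

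- Appendix 1, steps 20 to 22 and 42 to 44: no step measures off or retains foam, and 1.5 L appears only as a jar size.
- Jar size: step 1 gathers two 1.5 L jars and each receives about 0.9 L, so jar capacity does not limit the total.
- Section 9.5: a floor of 1.1 L and no ceiling.
- Synopsis, electrolyte assessment: drinking ends at the one-hour blood sample. This limits time, not volume.

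**5. Overdose text side by side.** Section 9.2 excludes the risk without condition. Sections 10.4 and 12.6 describe possible harm from a large volume, conditional on an existing small bowel problem. Section 5.4 adds that a large volume taken quickly may alter absorption of other medicines. The first statement is absolute and the others are not.

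**6. Earlier volumes side by side.** Section 5.4 reports what was drunk (up to 1.2 L). Section 7.3.2 reports what was requested (0.75 to 1.5 L) and a mean. Both can be true. Neither gives the highest volume drunk or how many of the 73 exceeded 1.2 L. The permitted 1.5 L is 0.3 L above the cited 1.2 L (1.5 / 1.2 = 1.25, or 25%).

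**The case against.** The best reply is that Appendix 1 summarises how to operate the mixing unit and is not a dosing instruction. The 1.5 L limit stands in the synopsis and in sections 7.1, 7.3.2 and 9.2, and section 9.1 ties administration to the protocol. Section 9.5 expects leftovers and weighs them. On this view the jars are a supply and the limit applies to what is drunk. That is partly right: no sentence asks a subject to finish both jars. It does not remove the conflict, because the synopsis and section 7.1 limit the volume provided, not only the volume drunk, and the appendix does more than prepare foam: it directs staff to give it to the subject.

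A reader might infer four stronger things that the documents do not support.

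- *That subjects will receive a 1.8 L dose.* The 1.8 L is a nominal volume handed over. Intake is still limited to 1.5 L elsewhere.
- *That 5.4 and 7.3.2 contradict each other.* One gives volume drunk and the other volume requested.
- *That the protocol presents volumes above 1.2 L as known to be safe.* Section 5.4 claims nothing above 1.2 L, and safety and tolerability is a secondary objective.
- *That the ileus warning disproves the overdose sentence.* The warning depends on an existing bowel condition, stands in different sections, and concerns a state that the exclusion for suspected ongoing disease should largely screen out. What remains is an unqualified sentence that does not fit the later text.

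The Investigator Brochure, to which section 5.3 refers, may contain the earlier volumes. If so, that part is easily closed, but the protocol's own statement still stops at 1.2 L.

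**Conclusion.** The point holds as an internal inconsistency. The volume handed over under section 9.1 and Appendix 1 is nominally 1.8 L, which is 0.3 L or 20% above the stated 1.5 L (19% to 23% over the yield range), and neither the appendix nor section 9.5 carries an upper limit. This rests on the protocol's own yield, on both batches being handed over whole as written, and on preparation losses well below 17%.

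The overdose sentence needs to be reconciled with 10.4 and 12.6. The 1.2 L statement in 5.4 is an evidence gap relative to the permitted 1.5 L and should be closed with the volumes actually drunk. None of this shows that 1.5 L is unsafe or that subjects will exceed it. Which volume or rule is right is for the sponsor to decide.

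**What to change.** - Reconcile the synopsis, sections 7.1, 7.3.2, 9.1, 9.2 and 9.5, and Appendix 1, so that the check before dispensing and the handover steps carry the same maximum as the rest of the protocol, whichever the sponsor confirms. Say what happens to foam above it.
- Reconcile the overdose sentence in 9.2 with 10.4 and 12.6.
- In 5.4, state the volumes actually drunk in LUM-001 and LUM-002, including the highest and the number of subjects above 1.2 L, relative to the range permitted here. Section 7.3.2 reports a mean, so the individual volumes should be on file.
- Optionally, list adverse events and electrolyte changes for each subject beside the volume drunk, which section 9.5 already records. Section 13.4 plans only general descriptive summaries.

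The cost is protocol wording, a look-up in completed trials and, if wanted, one listing for 10 subjects. No new data are collected and the sample size does not change.

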6 TRIAL OBJECTIVES

6.1 Primary Objective

To evaluate if Lumentin® 44 used as a small bowel filling agent in MRE examination generates images with acceptable diagnostic quality.

6.2 Secondary Objectives

- To evaluate plasma electrolytes including, potassium, sodium, phosphate, and calcium, as well as ionized calcium concentration levels during 24 hours after intake of Lumentin® 44.
- To evaluate bowel filling properties (extension and distension) of Lumentin® 44.
- To evaluate the safety and tolerability of Lumentin® 44 intake.

